This material is the property of the Mayo Clinic. Do not disclose or use except as authorized.

- Inclusion and exclusion criteria
- Complete medical and surgical histories
- Record of concomitant medication usage, including use of prescription and over-the-counter medications, and vitamin and/or mineral supplements
- Patient demographics
- Completion of questionnaires: Alcohol Use Disorder Identification Test (AUDIT), Alcohol Use- NIAAA Six Question Set
- Alcohol consumption for the last 30 days assessed using the Timeline Follow Back Questionnaire
- Vital signs (blood pressure, pulse, respiratory rate, and temperature)
- Complete physical examination, including height, weight, and BMI
- 12-lead ECG
- Liver biopsy (if performed)
- Chest X-ray
- Assessment of MELD Score
- Calculate Maddrey Score
- Clinical chemistry, hematology, coagulation, lipid profile, CRP, SAA1 Nutritional Assessment and correction as necessary
- Evaluation by Addiction Services and Social Services to outline rehabilitation plan for alcohol abuse. This may include pharmacotherapy.
- Nutritional Assessment
- Immunogenicity Testing
- Urinalysis
- Serum pregnancy test (for women of childbearing potential)
- Collection of specimens (blood and urine) for bio-specimen banking (optional)

The following study evaluations will be performed during the course of Dosing Day 1 (± 1):

- Review of inclusion and exclusion criteria
- Update medical and surgical histories
- Assess for Adverse Events
- Update record of concomitant medication usage, including use of prescription and over-the-counter medications, and vitamin and/or mineral supplements
- Vital signs (blood pressure, pulse, respiratory rate, and temperature) pre-dose then 3 hours post-infusion with blood pressure and heart rate monitoring every 30 minutes. Weight and BMI
- Assessment of MELD Score and recording of Lille score parameters
- Clinical chemistry, hematology, and coagulation prior to study drug dosing
- Urine pregnancy test (for women of childbearing potential)
- Receive first dose of study drug
- Pharmacokinetic testing
- Confirmation that patient is abstinent from alcohol

The following study evaluations will be performed during Day 3 (± 1 day):

- Update medical and surgical histories
- Update record of concomitant medication usage, including use of prescription and over-the-counter medications, and vitamin and/or mineral supplements
- Update Adverse Events

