- Vital signs (blood pressure, pulse, respiratory rate, and temperature)
- Weight and BMI
- Calculation of MELD Score
- Clinical chemistry, hematology, and coagulation
- Pharmacokinetic testing
- Confirmation that patient is abstinent from alcohol

The following study evaluations will be performed during the course of Dosing Day 7 (± 3 days):

- Update medical and surgical histories
- Update record of concomitant medication usage, including use of prescription and over-the-counter medications, and vitamin and/or mineral supplements
- Confirmation that patient is abstinent from alcohol
- Update Adverse Events
- Vital signs (blood pressure, pulse, respiratory rate, and temperature) pre-dose then 3 hours post-infusion with blood pressure and heart rate monitoring every 30 minutes.
- 12-Lead ECG
- Complete physical examination, including weight and BMI
- Calculation of MELD Score
- Calculation of Lille Score
- Clinical chemistry, hematology, coagulation, lipid profile, CRP, SAA1, total protein and albumin prior to study drug dosing
- Urine pregnancy test prior to study drug dosing
- Receive second dose of study drug
- Pharmacokinetic testing
- Collection of specimens (blood and urine) for bio-specimen banking
- Nutritional Assessment

The following study evaluations will be performed during the *Follow-up* Day 14 (± 3 days):

- Update medical and surgical histories
- Update record of concomitant medication usage, including use of prescription and over-the-counter medications, and vitamin and/or mineral supplements
- Confirmation that patient is abstinent from alcohol
- Update Adverse Events
- Vital signs (blood pressure, pulse, respiratory rate, and temperature)
- Weight and BMI

CONFIDENTIAL

This material is the property of the Mayo Clinic. Do not disclose or use except as authorized.

- Calculation of MELD Score
- Clinical chemistry, hematology and coagulation
- Pharmacokinetic testing
- Immunogenicity Testing
- Collection of specimens (blood and urine) for bio-specimen banking

The following study evaluations will be performed during the course of *Dosing Day 14* (± 3 days):

- Update medical and surgical histories
- Update record of concomitant medication usage, including use of prescription and over-the-counter medications, and vitamin and/or mineral supplements
- Confirmation that patient is abstinent from alcohol
- Update Adverse Events

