4.3 Treatment Regimen

F-652 will be administered by slow intravenous infusion over approximately 100 minutes. The study medication is reconstituted as per the protocol in 100 ml of 5% dextrose in water. To monitor, as well as prevent hypersensitivity reactions, the infusion rate will be as follows:

1. 10 ml/hr for 15 minutes
2. 20 ml/hr for 15 minutes
3. 40 ml/hr for 15 minutes
4. 80 ml/hr for 15 minutes
5. 100 ml/hr until infusion complete

That is, the total infusion will be over approximately 100 minutes. Patients will be monitored for 3 hours post-infusion with blood pressure and heart rate monitoring every 30 minutes.

CONFIDENTIAL

This material is the property of the Mayo Clinic. Do not disclose or use except as authorized.

Patients will receive two separate IV infusions separated by 6-10 days (i.e. one infusion on Day 1 and a repeat infusion approximately one week later depending on outpatient scheduling). After information is received regarding the primary end point (safety) at the first dose (10ug/kg), and the 10ug/kg dose determined to be safe, the 2nd cohort of patient will be administered the 30ug/kg dose. Further escalation will follow this scheme. If evaluations demonstrate safety and efficacy signals, patients in the final dose escalation cohort will receive a third dose of the study drug at the maximum tolerated dose on Day 14.

Medications allowed: Corticosteroids, pentoxifylline, antibiotics, acamprosate, and Baclofen, as well as any other medication deemed to be essential for the treatment of the patient will be allowed.

Prohibited medications: Biological agents and any other concomitant investigational agents.

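### Section 4.3 sets 6-10 days between the two infusions, but the Day 7 (± 3 days) dosing window allows 3-9 days, and nothing says which rule governs

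*Combined protocol and SAP*

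**What the plan says.** Three places in the protocol govern the timing of the second infusion.

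- **Section 4.3, Treatment Regimen:** "Patients will receive two separate IV infusions separated by 6-10 days". It explains this as "one infusion on Day 1 and a repeat infusion approximately one week later depending on outpatient scheduling".
- **Section 2.1, Trial Design:** the second dosing visit is introduced with "performed during the course of Dosing Day 7 (± 3 days", and its list of activities includes "Receive second dose of study drug". The first dosing visit has its own window ("during the course of Dosing Day 1 (± 1") and includes "Receive first dose of study drug".
- **Section 2.2, Schedule of Procedures:** repeats the ± 3 day window for Day 7 and the ± 1 day window for Day 1, and marks study drug dosing at both visits.

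Section 2.4 gives the nominal dosing days as Day 1 and Day 7. None of these places refers to another, and none says that the interval in Section 4.3 narrows or overrides the visit window.

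**The concern.** Both statements are instructions about when to give the same infusion, and they permit different sets of days. Site staff usually schedule from the visit table. A coordinator who does so can book the second infusion on Day 4, 5 or 6 without seeing a problem, although Section 4.3 calls for a longer gap. Section 9.1 requires monthly reports of deviations by site. With approximately six sites, the same dosing date could be counted differently from one site to the next.

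The interval also affects what is measured:

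- It determines how much of the first dose is still present at the second, and so the accumulation ratio, which Section 7.1 names as a PK output.
- It affects the CRP value drawn before the second dose. Section 1.5 says that CRP after the higher doses may peak 48-72 hours post-dose. A 3-day gap puts the pre-dose sample at the end of that period; a gap of 6 days or more puts it well past it. CRP is one of the efficacy-signal endpoints in Section 2.3.
- Section 1.6 plans three patients per dose level, so one or two short intervals could noticeably shift a cohort's PK or CRP summary.

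**Working it through.** **Step 1. Intervals allowed by each rule.** Gap = (day of dose 2) − (day of dose 1). The Day 7 window runs from 7 − 3 = Day 4 to 7 + 3 = Day 10. With dose 1 on Day 1, the gap runs from 4 − 1 = 3 to 10 − 1 = 9 days.

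| Gap (days) | Dose 2 on | Within Day 7 ± 3? | Within Section 4.3? |
|---|---|---|---|
| 3, 4, 5 | Day 4, 5, 6 | yes | no |
| 6, 7, 8, 9 | Day 7, 8, 9, 10 | yes | yes |
| 10 | Day 11 | no | yes |

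**Step 2. Can another reading reconcile the two?** The target is the 6-10 days of Section 4.3.

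- Dose 1 anywhere in Day 1 ± 1 (Day 0 to Day 2), with Day 7 held to the nominal calendar: from 4 − 2 = 2 to 10 − 0 = 10 days. Gaps of 2-5 days conflict.
- Dose 1 on Day 1 or Day 2 only: 2-9 days. Gaps of 2-5 days conflict, and 10 days is again outside the window.
- The window read as 7 ± 3 elapsed days: 4-10 days. Gaps of 4 and 5 days still conflict.
- The Section 4.3 interval read as full days between infusions, so that the dates differ by 7-11 days, against the 3-9 days of the window: gaps of 3-6 days conflict, and 10-11 days is outside the window.

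No reading reproduces 6-10 days.

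**Step 3. Size of the PK effect.** Section 1.4 reports half-lives of 39.4-206 hours, rising with dose, from single doses in healthy male volunteers. Assume one-compartment decay. The share of dose 1 left after d days is r(d) = 2^(−24d / t½).

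| Half-life | r(3 days) | r(6 days) | r(10 days) |
|---|---|---|---|
| 39.4 h | 0.282 | 0.079 | 0.015 |
| 206 h | 0.785 | 0.616 | 0.446 |

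The second-dose peak, in units of the first-dose peak, is 1 + r(d). Comparing the second-dose peak after 3 days with that after 6 days:

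- 39.4 h: 1.282 / 1.079 = 1.19
- 206 h: 1.785 / 1.616 = 1.10

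These two values do not bound the effect. Write x = r(3), so that r(6) = x² and the ratio is (1 + x) / (1 + x²). This is largest where 1 − 2x − x² = 0, that is x = √2 − 1 = 0.414. The ratio there is 1.414 / 1.172 = 1.21, at a half-life of 72 × ln 2 / 0.881 ≈ 57 h, which lies inside the reported range. Over 39.4-206 h the second-dose peak after 3 days is therefore about 10-21% higher than after 6 days.

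**The case against.** The strongest reply is that the two rules can be applied together. One sets a visit window and the other sets the spacing of infusions. They overlap at 6-9 days, and the nominal Day 1 and Day 7 schedule, a 6-day gap, meets both. The approximate 7-day spacing that Section 1.8 gives for the expansion cohort also points to about a week. Part of this stands: a careful site can satisfy both rules, and Section 4.3 excludes shorter gaps by implication, not by an express prohibition. But the protocol does not tell sites to apply both rules, and the schedule carries no cross-reference to Section 4.3.

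Some stronger conclusions are tempting but not supported:

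- **That the conflict distorts DLT counting.** Section 1.6 bases the MTD on DLT in the first cycle and does not define a cycle. If each infusion is a cycle, the gap before dose 2 cannot affect first-cycle DLTs. Any effect is conditional on that definition.
- **That the interval matters most at 45 µg/kg.** Half-life rises with dose, so the residual share is largest there. But the longest reported half-life gives the smallest relative change in second-dose peak, about 10%.
- **That the accumulation ratio will be computed from nominal times.** Nothing says so. A pre-dose PK sample is scheduled on Day 7, and Section 12.4 requires dosing dates as source data, so carry-over can be measured.
- **That the Day 7 Lille score adds to this conflict.** Its timing depends on the width of the visit window, which is a separate matter from the disagreement with Section 4.3.

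The 2-10 day range is also arguable. It needs dose 1 to move while Day 7 stays on the nominal calendar, whereas Sections 1.8 and 7.1 count follow-up from the first dose. The conflict does not depend on it.

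**Conclusion.** The contradiction is real and the text is wrong as written. With dose 1 on Day 1, three of the seven days in the second-dose window (Days 4, 5 and 6) fall outside Section 4.3, and one gap that Section 4.3 accepts (10 days) falls outside the window. This rests on day arithmetic alone.

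The PK size is illustrative: about 10-21% on the second-dose peak for a 3-day against a 6-day gap. It assumes one-compartment decay and that single-dose half-lives in healthy men carry over to patients with alcoholic hepatitis, which the documents do not establish. The main safety summary in Section 7.1 does not use the interval directly. The effect falls on PK, the pre-dose CRP value and the classification of deviations.

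**What to change.** Reconcile the Day 1 and Day 7 visit windows in Section 2.1, the Schedule of Procedures in Section 2.2 and the interval in Section 4.3, so that a single rule governs the gap between infusions. Count that gap between actual infusion dates, and rewrite the visit window to match. It would help to state in the PK analysis that actual infusion and sampling times are used; this is a clarification, not the correction of a stated error. Which interval is right is for the sponsor to decide, and none is proposed here.

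The change is to protocol wording only. Its cost is some loss of scheduling flexibility at the sites.

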4.4 Preparation and Administration of Study Drug

Reconstitution of F-652:

Remove the F-652 vial from the refrigerator. Using an appropriately sized syringe and needle, withdraw 1.0 mL of water for injection. Reconstitute the vial by slowly adding the 1.0 mL of water for injection into the interior of the vial's neck. Gently dissolve the drug powder with a slow swirling motion. This results in a solution of F-652 at a concentration of 5 mg/mL. Allow up to 2 minutes for the F-652 to dissolve. The solution should not be used if discolored or cloudy, or if particulate matter remains.

IV Preparation:

The research or clinical pharmacist will withdraw a volume of Baxter 5% Glucose IV solution and insert into the Baxter Empty Viaflex bag (PVC) 150mL. Based on the weight dose provided by the study team, withdraw the required volume of F-652 from the vial containing 5 mg/mL F-652 drug solution. Slowly add the appropriate volume of F-652 into the Baxter Empty Viaflex bag 150 mL containing 5% dextrose in water (D5W) to make the volume up to 100 mL, then gently invert the IV bag up to 5 times to ensure that the investigational product and Baxter 5% Glucose IV solution are well mixed.

Investigational Product at Study Site:

Study medication will be shipped to each institution site upon site initiation. The Investigator is responsible for monitoring the inventory of medication supplies, in order to ensure sufficient supply for the site. The study monitors will also verify the drug accountability during each site-monitoring visit. At the end of the study, all study drug supplies will be returned to the Sponsor/designee by the study monitor for each site.

Test Article Accountability:

The Investigator will maintain accurate records of the receipt of all study medication. In addition, accurate records will be kept regarding when and how much study medication is dispensed and used by each subject in the study. Drug accountability and distribution of drug will be done at each visit as needed during the course of the study. Reasons for deviation from the expected dispensing regimen must also be recorded. A storage temperature log is to be maintained to document proper storage conditions. Malfunctions must be reported to the sponsor immediately. The clinical supplies for this study must be maintained under adequate security and stored under conditions specified on the label.

Investigational Product at Study Site at Study Conclusion:

At completion of the study, all study medication will be reconciled by the designee and then returned, retained, or destroyed according to applicable country regulations. Prior to any action being taken with study medication after the study is completed; the investigator will contact the Generon Corporation, Ltd. or the contracted CRO for approval of such action.

4.5 Immunogenicity Testing

Immunogenicity testing will occur at Baseline, on Day 14, Day 28 and Day 42. Three assays will be used to evaluate the anti-F-652 antibodies in serum samples collected in this trial. The first assay is a Bridging ELISA binding assay which screens antibody binding activities in the serum samples. Positive samples identified in the binding assay will be analyzed in the confirmatory assay, in which a serum sample is first incubated with F-652 in vitro, and the sample is then analyzed by the binding assay. Positive samples identified in the confirmatory assay will be further analyzed in the cell-based neutralizing assay, in which the neutralizing bioactivity to F-652 (IL-22) in the serum samples is analyzed. The binding and confirmatory assay have been developed and validated in minimal required dilution (MRD), cut point and cut point correction factor, sensitivity, specificity, selectivity, inter and intra precision, and drug tolerance followed “Guidance for Industry, Assay Development for Immunogenicity Testing of Therapeutic Proteins” (FDA, CMC, 2009). The neutralizing assay has been developed and under validating. The validation reports have been sent to FDA in the IND 121673 Serial Number 0004.

5 Assessment of Efficacy Signals

5.1 Efficacy Parameters

- Change in MELD score, Lille score, triglycerides, CRP, AST, ALT and SAA1.

5.2 Method and Timing

1. MELD score will be calculated at each visit.
2. Lille score will be calculated on Day 7.

CONFIDENTIAL

This material is the property of the Mayo Clinic. Do not disclose or use except as authorized.

3. Triglycerides, CRP and SAA1 will be collected at Screening, Day 7, Day 14 (if dosed) and Day 28.
4. AST and ALT will be collected at Screening, Day 3, Day 7, Day 14, Day 28, Day 35, Day 42 and Day 56 (if applicable).
5. Adverse events will be evaluated at each study visit per the Schedule of Procedures by the study coordinator and reviewed by the investigator

6 *Assessment of Safety*

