We define response to the study drug as a decrease in the AST/ALT or serum triglycerides by 30% or more from baseline to Day 42 or Day 56. We will evaluate the patients' response rate for each cohort in phase I. If at the MTD level, the response rate is seen in only 1 of the 3 patients, an additional group of 6 patients will be recruited and treated at the MTD dose level. If efficacy signals can yet not be demonstrated in 2 or more of the 6 patients, the drug will be deemed ineffective. If efficacy signals are demonstrated at the highest safe dose, patients in the final cohort will be administered a third dose (10mcg/kg, 30 mcg/kg, or 45mcg/kg) of the MTD on Day 7 (± 3 days) following the second dose to determine if efficacy can be increased with additional dosing.

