2.2 Study Design/Type

Schedule of Procedures

Safety Assessments	Screening (-72 hrs)	Day 1 (± 1 day)	Day 3 (± 1 day)	Day 7 (± 3 days)	Day 14 (± 3 days)	Day 28 (± 4 days)	Day 42 (± 2 days)	Day 56 ⁶ (± 2 days)
Inclusion/Exclusion Criteria	X	X						
Physical Examination	X			X	X ⁵	X	X	X
Medical/Surgical History	X		X	X	X	X	X	X
Nutritional Assessment	X				X ⁵		X	X
AUDIT and NIAAA Questionnaires	X							
Timeline Followback Questionnaire	X					X	X	X
Vital Signs	X		X		X	X	X	X
Serial Vital Signs		X		X	X ⁵			
Serum Chemistry ^A	X	X	X	X	X	X	X	X
Coagulation ^A	X	X	X	X	X	X	X	X
Hematology ^A	X	X	X	X	X	X	X	X
Serum pregnancy test	X							
Urine pregnancy test		X		X	X ⁵			
Lipid profile, CRP, SAA1, total protein, albumin ^A	X			X	X ⁵	X		
Calculate MELD Score	X	X	X	X	X	X	X	X
Calculate Lille Score				X				
Calculate Maddrey Score	X							
Urinalysis ¹	X							
ECG ²	X			X	X ⁵	X		
Chest X-ray ³	X							
Adverse Events		X	X	X	X	X	X	X
Concomitant Medications	X	X	X	X	X	X	X	X
Study Drug Dosing		X		X	X ⁵			
Pharmacokinetic Sample Collection ⁷		X	X	X	X	X	X	
Immunogenicity Testing ⁸	X				X	X	X	
Biomarkers(blood and urine)	X ⁷			X	X	X	X	X
Confirmation that patient is abstinent from alcohol		X	X	X	X	X	X	X

1. Urinalysis results can be used for Screening if tested within 7 days.
2. ECG results can be used for Screening if tested within 7 days.
3. Chest X-ray results can be used for Screening if tested within 30 days.
4. Day 1, Day 7 and Day 14 labs and testing must be completed prior to dosing.
5. These tests/procedures will occur only on Day 14 if the patient is receiving a 3rd dose at that visit.
6. Day 56 will only occur if the patient received a 3rd dose on Day 14.
7. Biomarkers are optional at Screening.

^AClinical Laboratory Tests

Hematology	Coagulation	Serum Chemistry		Urinalysis	Other
		Liver Function Tests	Other Chemistry		
Complete Blood Count with differential, Platelet count, MCV	PT, INR	AST, ALT, Total Bilirubin, Direct Bilirubin	Sodium, Potassium, Chloride, Bicarbonate, Calcium, Magnesium, Phosphate, Creatinine, BUN, Glucose, Total protein, Albumin, Lipid profile, CRP, SAA1	Specific gravity, pH, Blood, Protein, Glucose, Ketones	β-HCG serum pregnancy test Urine pregnancy test

Blood will be collected for PK sampling per the schedule below:

⁸Pharmacokinetic Sampling Schedule

Study Visit Day					Study Visit Day +0*	Study Visit Day +2*	Study Visit Day +3*	Study Visit Day +4*
					24 hrs	48 hrs	72 hrs	96 hrs

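### Triglycerides, CRP and SAA1 have no defined baseline: Section 5.2 and their schedule row give only a Screening value before drug, while the laboratory panel table implies a pre-dose Day 1 draw

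*Combined protocol and SAP*

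**What the plan says.** Section 5.2, item 3, reads: "Triglycerides, CRP and SAA1 will be collected at Screening, Day 7, Day 14 (if dosed) and Day 28". The Schedule of Procedures in Section 2.2 has a separate row, "Lipid profile, CRP, SAA1, total protein, albumin", marked at Screening, Day 7, Day 14 (third dose only) and Day 28, and blank on Day 1.

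The visit lists in Section 2.1 follow the same pattern. Screening has "Clinical chemistry, hematology, coagulation, lipid profile, CRP, SAA1 Nutritional Assessment and correction as necessary", while Day 1 has only "Clinical chemistry, hematology, and coagulation prior to study drug dosing".

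The Clinical Laboratory Tests table below the schedule differs. It places lipid profile, CRP and SAA1 in the Serum Chemistry panel. The Serum Chemistry row is marked at every visit including Day 1, and a footnote requires Day 1 laboratory work to be finished before dosing.

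Triglycerides also enter the responder rule in Section 1.6 (Dose Expansion cohort): "We define response to the study drug as a decrease in the AST/ALT or serum triglycerides by 30% or more from baseline". That section judges the fall at Day 42 or at Day 56, whereas Section 7.1 uses Day 42. No section says which sample is the baseline for these three markers.

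For transaminases, Section 5.2, item 4, says: "AST and ALT will be collected at Screening, Day 3, Day 7, Day 14, Day 28, Day 35, Day 42". The list ends with a Day 56 draw where that visit applies. Day 1 is absent and Day 35 is present.

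**The concern.** Section 2 names CRP, SAA and triglycerides as the biomarkers of IL-22 activity. Sections 2.3 and 5.1 make change in them an efficacy signal, and Section 7.1 models them over time. There is no concurrent control, so change from baseline is the only evidence of effect on these markers. The last pre-drug value therefore matters more than it would in a randomised trial.

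The Screening-to-Day 1 interval is not a quiet one. Section 2.1 puts nutritional correction and the addiction and social services evaluation in Screening. Section 3.1 admits patients who drank within the previous 6 weeks, and abstinence is first confirmed on Day 1. Corticosteroids are allowed (Sections 3.1 and 4.3). If the baseline is the Screening sample, any movement from these causes before the first infusion is read as drug effect. If some sites follow the panel table and others the dedicated row, baselines will also differ between patients in a trial of about 18.

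**Working it through.** The plan gives no figure on this point. The sample-size figure in Section 1.9 does not depend on it. The check is a comparison of the places that say when the three markers are drawn.

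| Source | Screening | Day 1 | Day 7 | Day 14 | Day 28 | Day 42 | Day 56 |
|---|---|---|---|---|---|---|---|
| Section 5.2, item 3 | yes | no | yes | if dosed | yes | no | no |
| Dedicated schedule row | yes | no | yes | third dose only | yes | no | no |
| Section 2.1 visit lists | yes | no | yes | dosing visit only | yes | no | no |
| Panel table, through the Serum Chemistry row | yes | yes | yes | yes | yes | yes | third dose only |

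**Which reading has more support.** Three sources leave Day 1 blank. Section 15 also points that way: it lists lipid profile, CRP and SAA1 under Special Investigations, apart from Serum Chemistry. One source, the panel table, implies a Day 1 draw. The conflict is real and nothing in the text resolves it.

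**Length of the pre-drug interval.** Section 2.6 puts Screening within 72 hours of Day 1. The Day 1 window is plus or minus 1 day, so the longest interval is about 72 + 24 = 96 hours.

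**Direction.** Section 1.5 reports that F-652 raises CRP at 30 and 45 µg/kg. A fall in CRP between Screening and Day 1 would hide part of that rise. A fall in triglycerides over the same interval would look like response. The bias has no single sign.

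**Size.** The documents give neither within-patient variability nor pre-drug drift for any of the three markers, so the bias cannot be computed.

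**Which baseline to use (illustration only, all inputs assumed).** Take log-normal triglycerides, within-patient CV 20% to 40%, no drug effect, and a 20% fall between Screening and Day 1. The log SD is s = sqrt(ln(1 + CV²)), which is 0.198 to 0.385. The chance of an apparent fall of 30% or more is then:
- Screening baseline: Φ((ln 0.7 − ln 0.8)/(s√2)) = 32% to 40%.
- Mean of the Screening and Day 1 logs: Φ((ln 0.7 − ½ ln 0.8)/(s√1.5)) = 16% to 30%.
- Day 1 alone: Φ(ln 0.7/(s√2)) = 10% to 26%.

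Averaging keeps half of the drift, so under drift Day 1 alone does better. With no drift, averaging helps slightly (7% to 23%, against 10% to 26% for either single value). These figures serve only to choose between baselines. They do not estimate this trial's false-response rate.

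**AST/ALT days.** The Day 28 window runs from 28 − 4 = 24 to 28 + 4 = 32, and the Day 42 window from 42 − 2 = 40 to 42 + 2 = 44. Day 35 lies in neither. It is not a schedule column, not a visit in Section 2.1 and not an analysis day in Section 7.1. Day 1 is missing from the list, although the schedule draws serum chemistry that day and Section 6.2 assesses chemistry at each visit.

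**Follow-up triglycerides.** On the three-source reading the last draw is Day 28. Response is defined at Day 42 or Day 56, so the triglyceride part of the rule has no scheduled follow-up value.

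**The case against.** The strongest reply is that the panel table settles the matter: the three markers belong to Serum Chemistry, Serum Chemistry is drawn before dosing on Day 1, and so a proper baseline exists. Section 5.2 is also a poor witness, because it omits Day 1 for AST/ALT too, although those are plainly drawn that day. This part stands: silence in Section 5.2 alone does not prove that there is no Day 1 draw. It does not dispose of the point, because the dedicated row and the Section 2.1 list also leave Day 1 out, and baseline remains undefined on either reading.

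A second reply is that little would be gained. The interval is at most about four days, while abstinence, steroids and natural recovery act without a control until Day 42. That is correct, and it is why the point is minor. Removing the pre-drug part is still worthwhile because it is nearly free.

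A reader might infer that drift before drug inflates the apparent effect on all three markers. The documents do not support that: the CRP case runs the other way, and symmetric noise does not bias a mean change. A reader might also want a false-response rate for triglycerides. Any such rate would rest on assumed CVs and drifts, and on the three-source reading it would concern an endpoint with no Day 42 sample.

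The absence of a fasting instruction is a missing detail. Section 12.6 refers to instruction manuals that are not among the documents, so it should not be counted as an error. Day 35 is a stray entry that no analysis uses, not a lost endpoint.

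**Conclusion.** The point holds as an internal inconsistency and an undefined baseline. If Section 5.2 and the dedicated row are followed, up to 72 hours of pre-drug change, or about 96 hours with the Day 1 window, is included in the apparent effect on triglycerides, CRP and SAA1. Its sign depends on the marker and its size cannot be derived from the documents. The stronger statement, that the plan certainly has no Day 1 value and so overstates drug effect, goes further than the text, because the panel table can be read as supplying that value.

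The conclusion rests on two things: that no text outside these documents defines baseline, and that sites could reasonably follow the dedicated row. The severity is low. The mismatch between the Day 28 triglyceride draw and the Day 42 or Day 56 response is the larger gap at the same sentence and should be closed in the same edit.

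**What to change.** 1. State in Section 5.2, in the Day 1 list of Section 2.1 and in the dedicated schedule row that triglycerides, CRP and SAA1 are assayed on the pre-dose Day 1 blood. Make the panel table and Section 15 agree.
2. Define the pre-dose Day 1 value as baseline for these markers in Section 7.1. Use Screening only when Day 1 is missing, and do not average the two.
3. In the AST/ALT list of Section 5.2, delete Day 35 and add Day 1.
4. Reconcile the last listed triglyceride draw at Day 28 with the Day 42 or Day 56 response definition in Sections 1.6 and 7.1.

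Items 1 and 2 cost three assays on blood already being drawn in about 18 patients, plus wording. Item 3 is wording only. Item 4 needs either a later triglyceride assay on blood already scheduled for chemistry or a change to the definition. Recording fasting status would be useful but is optional. None of this removes improvement after Day 1 from abstinence, permitted treatment or natural course, and the report should say so.
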